### 5.4. Medication Phase

#### 5.4.1. Randomization and Medication Titration

Participants who are eligible after the physical exam will be randomized to one of three treatment conditions (VAR, NTX, or PLA). Urn randomization will be used to balance the groups by gender, smoking status (as reported on question 1 of the Fagerstrom Test for Nicotine Dependence), and drinking status ('heavy' drinker defined as 14 or more drinks per week for

males/7 or more drinks per week for females, or 'very heavy' drinker, defined as 35 or more drinks per week for males/28 or more drinks per week for females). The UCLA Research Pharmacy will manage the blind. The three treatment conditions will not be different in appearance or method of administration. All participants will undergo a week-long medication titration period prior to the onset of the practice quit attempt.

#### 5.4.2. Practice-Quit Attempt

During the practice-quit attempt, participants will be instructed to abstain completely from drinking alcohol during a 7-day practice quit period. This period will begin on Day 8 of study medication dosing. During this period, participants will complete daily online and phone visits to report on their drinking, mood and craving for alcohol during the previous day in a daily diary assessment (DDA). For each virtual visit, participants will be contacted over the phone by research staff. Participants will first be asked about adverse events (open-ended) and about use of concomitant medications. Research staff will then administer the CIWA-Ar to measure alcohol withdrawal. Next, they will ask participants to report on their past day drinking as well as cigarette and marijuana use. Finally, while participants are still on the phone, research staff will send a link to the daily diary assessment (administered via Qualtrics). Research staff will request that participants' report the completion of this assessment via phone call or text message. Upon confirmation of assessment completion, staff will schedule a time for the following day's virtual visit. Depending on interest and eligibility, participants may be asked to wear a sleep tracking wristband during the 7-day practice quit period. Participants will be reminded to sync wristband data to an app during the daily calls and instructed to only use the wristband for sleep tracking purposes. Staff will also request a picture of the medication blister pack to monitor medication compliance. This procedure has been designed to maintain study integrity while reducing participant safety burden by limiting direct, in-person contact.

#### 5.4.3. Study Medication

On Day 1, participants will report to the laboratory to complete the alcohol cue-reactivity paradigm and receive their first medication dose under direct observation of study staff. They will receive a 7-day supply of study medication in blister packs with AM and PM dosing clearly distinguished for the titration procedure. After reaching full medication dose at the end of one week, participants will come to the laboratory on Day 8 to receive their second, 7-day supply of study medication and to begin the 7-day practice quit attempt. Participants will be asked to take AM dose of study medication on Day 8 in the lab under direct observation of study staff. All study medication will be prepared by the UCLA Research Pharmacy and will be identically matched in appearance (opaque capsules) and the medication labels will not reveal the drug identity.

##### 5.4.3.1. Dosing Schedule

Group:	NTX		VAR		PLA	
	Day:	AM	PM	AM	PM	AM
Medication Titration						
1	1 capsule (12.5mg NTX)	1 capsule (placebo)	1 capsule (0.5mg VAR)	1 capsule (placebo)	1 capsule (placebo)	1 capsule (placebo)
2	1 capsule (12.5mg NTX)	1 capsule (placebo)	1 capsule (0.5mg VAR)	1 capsule (placebo)	1 capsule (placebo)	1 capsule (placebo)
3	1 capsule (12.5mg NTX)	1 capsule (placebo)	1 capsule (0.5mg VAR)	1 capsule (placebo)	1 capsule (placebo)	1 capsule (placebo)

4	1 capsule (25mg NTX)	1 capsule (placebo)	1 capsule (0.5mg VAR)	1 capsule (0.5mg VAR)	1 capsule (placebo)	1 capsule (placebo)
5	1 capsule (25mg NTX)	1 capsule (placebo)	1 capsule (0.5mg VAR)	1 capsule (0.5mg VAR)	1 capsule (placebo)	1 capsule (placebo)
6	1 capsule (25mg NTX)	1 capsule (placebo)	1 capsule (0.5mg VAR)	1 capsule (0.5mg VAR)	1 capsule (placebo)	1 capsule (placebo)
7	1 capsule (25mg NTX)	1 capsule (placebo)	1 capsule (0.5mg VAR)	1 capsule (0.5mg VAR)	1 capsule (placebo)	1 capsule (placebo)
Practice Quit Attempt						
8	1 capsule (50mg NTX)	1 capsule (placebo)	1 capsule (1mg VAR)	1 capsule (1mg VAR)	1 capsule (placebo)	1 capsule (placebo)
9	1 capsule (50mg NTX)	1 capsule (placebo)	1 capsule (1mg VAR)	1 capsule (1mg VAR)	1 capsule (placebo)	1 capsule (placebo)
10	1 capsule (50mg NTX)	1 capsule (placebo)	1 capsule (1mg VAR)	1 capsule (1mg VAR)	1 capsule (placebo)	1 capsule (placebo)
11	1 capsule (50mg NTX)	1 capsule (placebo)	1 capsule (1mg VAR)	1 capsule (1mg VAR)	1 capsule (placebo)	1 capsule (placebo)
12	1 capsule (50mg NTX)	1 capsule (placebo)	1 capsule (1mg VAR)	1 capsule (1mg VAR)	1 capsule (placebo)	1 capsule (placebo)
13	1 capsule (50mg NTX)	1 capsule (placebo)	1 capsule (1mg VAR)	1 capsule (1mg VAR)	1 capsule (placebo)	1 capsule (placebo)
14	1 capsule (50mg NTX)	-	1 capsule (1mg VAR)	-	1 capsule (placebo)	-

#### 5.4.4. Alcohol Cue Reactivity Sessions (CR)

Randomized participants will complete a cue-exposure paradigm at two time points during the study, once on Day 1 prior to ingesting the first dose of study medication, and again on Day 14, approximately 90 minutes after study drug administration. Alcohol cue exposure will follow well-established experimental procedures. Sessions will begin with a 3-minute relaxation period. Participants will then hold and smell a glass of water for 3 minutes to control for the effects of simple exposure to any potable liquid. Next, participants will hold and smell a glass of their preferred alcoholic beverage for 3 minutes. Order is not counterbalanced because of carryover effects that are known to occur. Participants (who are smokers) will be allowed a smoke break immediately prior to the CR assessment. After every 3 minutes of exposure, participants will rate their urge to drink on the Alcohol Urge Questionnaire (AUQ) and their mood on the Profile of Mood States (POMS). AUQ score (alcohol minus water) is the primary outcome for the CR.

#### 5.4.5. Behavioral Economics Procedure

Participants will complete the behavioral economic protocol at the final day of the practice quit attempt (Day 14). Specifically, the multiple-choice procedure and measures will be completed after the cue-reactivity procedure in order to maintain the scientific integrity of the trial. The primary behavioral economic measure is the multiple-choice protocol. The multiple-choice protocol consists of choices between immediate alcohol (a single standard-sized drink of the participant's preferred alcoholic beverage, available today) and 17 delayed monetary reward amounts in the form of cash or electronic gift card (1¢, 5¢, 10¢, 25¢, 50¢, \$1, \$1.50, \$2, \$3, \$4, \$5, \$6, \$8, \$10, \$15, \$20, and \$30, available after one week). Participants will receive one randomly selected choice from the multiple-choice protocol. Participants will select a poker chip from a bowl containing chips pertaining to all of their choices on the multiple-choice protocol. A computerized random number generator program may be used in lieu of the poker chips if COVID safety regulations require. If the participant's choice on that item is for alcohol, they will receive one standard drink at that moment. If their choice is for the delayed money, they will

receive the money in cash or electronic gift card after one week. All participants will remain in their respective visit room for a 15-minute consumption period. Participants who receive alcohol are permitted to consume their beverage during this time. This will be followed by a recovery period in a laboratory lounge. The order of presentation will be multiple-choice procedure, hypothetical delay discounting task (Monetary Choice Questionnaire), and the hypothetical purchase task (Alcohol Purchase Task). Completion of the multiple-choice paradigm and hypothetical measures will take approximately 30 minutes. All participants will be required to stay in the laboratory for at least 1.5 hours after completing measures and the multiple-choice procedure. This will be done to standardize the procedure and prevent participants from choosing money instead of alcohol to limit the amount of time spent in the laboratory. Participants will be required to remain in the laboratory until BrAC reaches 0.00 g/dl.

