## **3. STUDY OBJECTIVES**

### **3.1. Specific Aims**

Primary Aim #1: To test whether NTX (50 mg) or VAR (2 mg) results in a (a) higher percentage of days abstinent and (b) lower number of drinks per drinking day during the 7-day practice quit attempt, as compared to placebo.

Primary Aim #2: To test whether NTX (50 mg) or VAR (2 mg) reduces cue-induced craving for alcohol, as compared to placebo. This aim allows us to confirm NTX effects using an established and widely studied paradigm.

Primary Aim #3: In order to validate this early efficacy paradigm, we will test the association between medication effects on cue-reactivity in the laboratory and drinking behavior during the practice quit attempt.

Secondary Aim #1: To determine whether the effects of medication on the multiple-choice paradigm are mediated by changes in discounting or demand for alcohol.

[figure not shown]
Secondary Aim #2: To determine whether the number of drinks per drinking day and percentage of days abstinent during the practice quit attempt predict alcohol choice.

Exploratory Aim: In order to test medication efficacy, we will directly compare NTX and VAR on percentage days abstinent and number of drinks per drinking day during the 7-day practice quit attempt.

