## 6. ASSESSMENTS

### 6.1. Schedule of Assessments Table

STUDY VISIT:	Initial Screening	Medical Screening	CR Sessions (Days 1 & 14)	Randomization (Day 1)	Practice Quit (Days 8-14)
SCREENING/INDIVIDUAL DIFFERENCE MEASURES:					
Alcohol Dependency Scale (ADS)				x	
Beck Anxiety Inventory (BAI)				x	x*
Beck Depression Inventory (BDI)				x	x*
Brief AUD Severity Scale				x	
Cannabis Use Disorder Identification Test (CUDIT)				x	
Demographics	x				
Fagerstrom Test for Nicotine Dependence (FTND)	x				
Family Tree Questionnaire (FTQ)				x	
Graded Chronic Pain Scale				x	
ImBIBe				x	
Inventory of Drinking Situations (IDS)				x	
Locator Form	x				
Monetary Choice Questionnaire (MCQ)				x	x*
Obsessive Compulsive Drinking Scale (OCDS)				x	x*
Penn Alcohol Craving Scale (PACS)				x	x*
Perceived Stress Scale (PSS)				x	
Pittsburgh Sleep Quality Index (PSQI)				x	x*
Readiness to Change (RTC) Ladder				x	
Self-Report Habit Index (SRHI) Drinking & Smoking				x	
Structured Clinical Interview for DSM-5 Screener & AUD Module	x				
Timeline Follow Back (TLFB)	x	x		x	x
UCLA Reward Relief Habit Drinking Scale (UCLA RRHDS)				x	
UPPS-P Impulsive Behavior Scale				x	
SAFETY MEASURES/BIOMARKERS:					
Adverse Events/SAFTEE					x
Alcohol Breathalyzer	x	x	x	x	x
Birth Control Assessment	x				
Clinical Institute Withdrawal Assessment (CIWA-AR)	x	x		x	x
Columbia Suicide Severity Rating Scale (C-SSRS)	x				
Comprehensive Metabolic Panel/Complete Blood Count		x			
Concomitant Medications	x	x		x	x
Electrocardiogram (EKG)		x			
Medical History/Physical Exam		x			
Urine Ethyl Glucuronide (EtG) Test					x
Urine Drug Screen	x	x		x	
Urine Pregnancy Test	x	x		x	x*
Vital Signs	x	x		x	x
EXPERIMENTAL MEASURES:					
Alcohol Purchase Task (APT)					x*
Alcohol Urge Questionnaire (AUQ)			x		
Daily Diary Assessment					x
Multiple Choice Procedure (MCP)					x*
Profile of Mood States (POMS)			x		

Sleep Tracking Wristband						x
*Measure collected on Day 14 only						

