#### **6.2.13. Monetary Choice Questionnaire (MCQ)**

The Monetary Choice Questionnaire is a 27-item self-administered questionnaire in which the participant chooses between a smaller, immediate monetary reward and a larger, delayed monetary reward. The MCQ will be completed at randomization and Day 14 visit, as part of the behavioral economics paradigm.

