#### **1.1.10. Alcohol Breathalyzer**

An alcohol breathalyzer will be administered at consent, and at every in-person study visit as a safety measure. BrAC must be equal to 0.000 prior to performing any study assessments. Results will be recorded on the paper checklist, and later entered into the database.

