### **1.1.23. Alcohol Purchase Task (APT)**

The Alcohol Purchase Task (APT) will be used to assess state-level alcohol demand during the behavioral economics paradigm at Day 14. The APT is a hypothetical assessment wherein participants report how many standard drinks they would immediately consume at 17 price points: free, 5¢, 10¢, 25¢, 50¢, \$1, \$1.50, \$2, \$3, \$4, \$5, \$6, \$8, \$10, \$15, \$20, and \$30. A hypothetical APT will be used given evidence that derived alcohol demand indices correlate with both self-reported drinking measures and alcohol consumption during actual purchase tasks.

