#### **3.2.4. Secondary Aim 1: Medication Effects on Alcohol Choice, Delay Discounting, and Alcohol Demand.**

One-way Analysis of Covariance (ANCOVAs) will be used to determine significant mean differences in crossover points on the multiple-choice paradigm, delay discounting, and alcohol demand between the medication groups (naltrexone, varenicline, and placebo). Mediation analyses will be used to determine whether the effects of medication on the multiple-choice paradigm were mediated by changes in discounting or demand for alcohol. Baseline covariates such as age, sex, and smoking status will be included in the model.

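### Secondary Aim 1 plans mediation through changes in discounting or demand, but demand has no baseline and both Day 14 mediators are measured after the choice outcome, so an indirect effect can only be exploratory

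*Combined protocol and SAP*

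**What the plan says.** Secondary Aim #1 in section 3.1 (Specific Aims) asks whether medication effects on the multiple-choice paradigm "are mediated by changes in discounting or demand for alcohol". The analysis section for that aim (3.2.4) first compares arms on crossover points, discounting and demand by ANCOVA. It then plans mediation analyses of whether "effects of medication on the multiple-choice paradigm were mediated by changes in discounting or demand for alcohol".

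The two candidate mediators are scheduled differently:

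- Discounting, by the Monetary Choice Questionnaire (MCQ): "The MCQ will be completed at randomization and Day 14 visit, as part of the behavioral economics paradigm" (section 6.2.13).
- Demand, by the Alcohol Purchase Task (APT): it "will be used to assess state-level alcohol demand during the behavioral economics paradigm at Day 14" (section 1.1.23). In the Schedule of Assessments (6.1) it has no entry at randomization, and its single entry carries the footnote "Measure collected on Day 14 only".

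Section 5.4.5 sets the Day 14 sequence: "The order of presentation will be multiple-choice procedure, hypothetical delay discounting task (Monetary Choice Questionnaire), and the hypothetical purchase task". One drawn choice is honoured, and it may be a standard drink. A 15-minute consumption period is described: "Participants who receive alcohol are permitted to consume their beverage during this time". That section does not place the draw or the drink relative to the MCQ and APT. The Alcohol Breathalyzer section (1.1.10) says "BrAC must be equal to 0.000 prior to performing any study assessments".

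**The concern.** There are two separate difficulties with the mediation aim. First, a change needs two readings and demand has one, so half of the stated mediator cannot be formed as worded. Second, the usual mediation argument needs the mediator to precede the outcome. Here the outcome comes first, and both post-treatment mediator readings follow it minutes later. Having just chosen between alcohol and delayed money on 17 items, a participant then answers questions on delayed money and on alcohol purchases at a series of prices. A tendency to answer consistently would be enough to create an apparent indirect effect.

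At stake is a mechanistic conclusion: that a medication alters choice by altering discounting or demand. The between-arm comparisons in the same section are not at risk.

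A smaller, conditional matter arises from the same procedure. Day 14 is the last day of the quit attempt, and the Timeline Follow Back (TLFB, section 1.1.6) covers days up to and including the last visit. No rule says whether a study-served drink counts toward percent days abstinent (PDA) or drinks per drinking day (DPDD).

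**Working it through.** **What can be computed from the schedule**

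| Measure | Day 1 | Day 14 | Within-person change | Day 14 arm comparison |
|---|---|---|---|---|
| MCQ (discounting) | yes | yes, second | yes | yes |
| APT (demand) | no | yes, third | no | yes |
| Multiple-choice procedure (outcome) | no | yes, first | no | yes |

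The Day 1 MCQ does not solve the order problem, because the change score still contains the Day 14 reading taken after the choices.

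**The plan's own figure.** The only power statement (section 3.1, Statistical Power) is for a one-way ANOVA with 3 groups, f = 0.40, alpha 0.05 and 90 completers. Noncentrality is 90 × 0.40² = 14.4 on 2 and 87 degrees of freedom, which gives power 0.926 against a stated 0.91 (printed with a stray percent sign). It agrees within 2 points, but it does not concern the mediation aim. The documents give no effect size for choice, so a range is used below.

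**Size of the order problem (assumed model).** Let choice be k = −d·arm + u, with u of unit variance. Let the later mediator reading be M = r·k + √(1 − r²)·e, so that M has no effect on k. Then:

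- arm to mediator: a = −r·d
- mediator to choice, given arm: b = r
- indirect effect: a·b = −r²·d; total effect: −d; share apparently mediated: r²

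For r = 0.3, 0.5 and 0.7 the share is 9%, 25% and 49%, although the true share is zero.

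The plan names no mediation test. Assuming a joint-significance test at 5% on each path, one active arm against placebo and 30 per arm, simulation (40,000 trials per cell) gives the proportion declaring mediation:

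| d | r = 0 | r = 0.3 | r = 0.5 | r = 0.7 |
|---|---|---|---|---|
| 0.3 | 0.2% | 4% | 9% | 13% |
| 0.5 | 0.2% | 5% | 16% | 27% |
| 0.85 | 0.2% | 10% | 36% | 62% |

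The last row is the planning f = 0.40 carried over to choice with both active arms equal: d = 0.40 × 3/√2 = 0.849. It is the most unfavourable of the three and should not be read alone.

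**Would reversing the order cure it?** Assume that neither measure affects the other, but that one medication-sensitive state drives both, with arm effect d on each and within-arm correlation r. The model is then the same whichever measure comes first. For r = 0.3, 0.5 and 0.7 the joint test declares mediation in about 58%, 88% and 90% of trials at d = 0.85, and in 30%, 47% and 48% at d = 0.5. Order is therefore one obstacle, and not the largest.

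**Served drink.** One counted drinking day moves a participant's PDA by 1/7 = 14.3 points. Two days at 5 drinks give DPDD 10/2 = 5.0; adding a one-drink Day 14 gives 11/3 = 3.7. If the share served differs between arms by 10, 20 or 30 points (assumed), and those served drink and would otherwise have been abstinent that day, mean PDA shifts by 14.3 × 0.10, 0.20 or 0.30 = 1.4, 2.9 or 4.3 points.

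**The case against.** The strongest reply is that the word for change need not mean a within-person score. Section 3.2.4 tests mean differences between randomized arms, and in a parallel randomized design a Day 14 difference in demand estimates the medication effect on demand without a baseline. Section 1.1.23 calls the APT a state measure, so the missing baseline may be deliberate. This largely stands: it reduces the first difficulty to wording and some lost precision. A reader might infer that the aim cannot be analysed at all, or that neither mediator has a baseline; the schedule contradicts both.

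Giving the multiple-choice task first is also defensible, because section 5.4.5 makes it the primary behavioral economic measure. A reader might infer that task order alone spoils the aim and that reordering would repair it. The shared-state calculation shows otherwise.

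A reader might also infer that the MCQ and APT are answered after drinking. The text does not settle this. The breathalyzer rule, and the total of about 30 minutes given for the choice task and both questionnaires, point towards completion before any drink.

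Finally, a reader might infer that the served drink contaminates the co-primary outcomes. Daily diaries and calls cover the previous day, so they would miss Day 14. The drink enters only if the TLFB is taken after the task and records it, and the breathalyzer rule read literally would delay such a TLFB until breath alcohol is back to zero. No passage says that this happens.

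None of these replies makes an indirect effect from this session causal.

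**Conclusion.** The point holds. As worded, the demand half of the mediator cannot be computed, and the data from this session cannot support a conclusion that discounting or demand mediates the medication effect on choice. That follows from the schedule and the stated task order alone.

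The false-mediation rates are illustrative. They rest on an assumed effect on choice, an assumed correlation and an assumed test. At d = 0.3 they are modest (4–13%); only at the borrowed planning effect do they exceed half of trials.

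The reach is limited to a secondary aim, and the arm comparisons of choice, discounting and Day 14 demand remain valid. The served-drink rule is a minor missing detail. If the drink were counted, Secondary Aim 2 (section 3.2.5) would predict choice partly from its own consequence, while the effect on Primary Aim 1 would be small under the shares assumed above. The change is worth making because it costs almost nothing.

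**What to change.** 1. In sections 3.1 (Specific Aims) and 3.2.4, replace the mediator wording with *change in discounting and Day 14 demand (baseline-adjusted for discounting only)*. Report discounting and demand as parallel medication outcomes, and label any indirect-effect estimate exploratory and non-causal.
2. Keep the multiple-choice task first. Reconcile section 5.4.5 with section 1.1.10 by stating that the MCQ and APT are completed before the draw and any drink. This removes one ambiguity; it does not make the mediation estimate causal.
3. State that study-provided alcohol is recorded separately and excluded from PDA and DPDD, whenever the TLFB is taken.
4. Optional, for participants still to be enrolled: add the APT on Day 1, after the cue-reactivity session and before the first dose, so that the craving baseline for Primary Aim 2 is not disturbed. Analyse it separately, as a baseline-adjusted sensitivity analysis.

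Cost: items 1 to 3 are a few sentences. Item 4 adds a short hypothetical questionnaire and gives a baseline for later enrollees only, so that analysis is smaller. Protocol changes need IRB approval before use (section 4.1.1). If enrolment is complete, items 1 and 3 can still be settled in the analysis plan. For item 2, the order actually followed should then be reported.

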#### 5.4.6. Brief Counseling Session

All participants will meet in-person or via an online platform with a trained study counselor briefly after the behavioral economics procedure, either on Day 14 or scheduled on a separate day shortly after the Day 14 visit depending on participant and counselor availability. This brief intervention draws from motivational interviewing and SBIRT models. It uses the therapeutic stance of motivational interviewing which is collaborative and client-centered. Consistent with the literature on brief intervention, the therapist will seek opportunities to engage in- and to amplify change talk. Together, the combination of evidence-based practices and principles applied to AUD, coupled with the experience of change in the context of study participation, is expected to result in an opportunity for health behavior change (i.e., reductions in alcohol use).

